#### 8.31 Lenalidomide dose adjustment for renal function

Lenalidomide dose will be adjusted as per standard of care guidelines in the prescribing information of lenalidomide for multiple myeloma patients. Patients with creatinine clearance (CrCl)  $<30$  ml/min noted while on treatment and not considered secondary to disease progression will have dose modifications as per the following guidelines. Patients with baseline CrCl  $<30$  ml/minute are not eligible for this study.

Table 8.32: Lenalidomide dose adjustment for baseline renal dysfunction

Creatinine Clearance (CrCl)	Lenalidomide Dose
CrCl $>60$ ml/minute	No adjustment required*
CrCl 30-60 ml/minute	10 mg once daily (may increase to 15 mg once daily after 2 cycles if nonresponsive but tolerating treatment)
CrCl $<30$ ml/minute (non-dialysis dependent)	15 mg every 48 hours

\*The starting dose would be as determined by the phase 1 of the trial. MTD will be utilized for phase 2 as long as the CrCl  $>60$  ml/minute and dose adjustments needed as per the table if CrCl  $<60$  ml/minute.

#### 8.4 Dexamethasone Dose Modifications

→ → Use the NCI Common Terminology Criteria for Adverse Events (CTCAE) version 4.0\* unless otherwise specified ← ←

CTCAE System/Organ/Class (SOC)	ADVERSE EVENT	AGENT	ACTION**
Metabolism and nutrition disorders	Hyperglycemia (despite adequate anti-hyperglycemic management) Grade 2	Dexamethasone	Treatment with insulin or oral hypoglycemics as needed
	Grade 3 or 4		
 
• Discontinue dexamethasone
 
 
* Can continue lenalidomide and ibrutinib as per protocol

CTCAE System/Organ/Class (SOC)	ADVERSE EVENT	AGENT	ACTION**
Gastrointestinal disorders	Upper gastrointestinal hemorrhage Grade 3 or 4 OR Lower gastrointestinal hemorrhage Grade 3 or 4		
 
• Discontinue dexamethasone
 
* Can continue lenalidomide and ibrutinib as per protocol
 

	Pancreatitis ≥ Grade 3 (Severe pain; vomiting; medical intervention indicated (e.g., analgesia, nutritional support))		
 
Discontinue dexamethasone and do not resume
 
* Can continue lenalidomide and ibrutinib as per protocol
 

Gastrointestinal disorders	Dyspepsia, gastric or duodenal ulcer, gastritis ≥Grade 3 (Severely altered GI function; TPN indicated; elective operative or endoscopic intervention indicated; limiting self-care ADL; disabling)	Dexamethasone	
Omit dexamethasone until symptoms adequately controlled Restart one dose level below along with concurrent therapy with H2 blockers, sucralfate, or omeprazole If symptoms persist despite above measures, discontinue dexamethasone and do not resume
 
Can continue lenalidomide and ibrutinib per protocol

Cardiac Disorders	Sinus bradycardia/ other cardiac Arrhythmia Grade 3 or 4		
Omit dose and follow at least weekly If the AE resolves to ≤Grade 2, implement one dose reduction step and continue therapy

General disorders and administration site conditions	Edema ≥Grade 3 (limiting function and unresponsive to therapy or anasarca)		
Diuretics as needed, and decrease dexamethasone dose by 1 dose level If edema persists despite above measures, decrease dose another dose level Discontinue dexamethasone and do not resume if symptoms persist despite second reduction Ibrutinib and lenalidomide should be continued.

Psychiatric disorders	Confusion or Mood alteration ≥ Grade 2 (Severe disorientation; limiting selfcare ADL)		
Omit dexamethasone until symptoms resolve Restart with one dose level reduction If symptoms persist despite above measures, discontinue dexamethasone and do not resume Ibrutinib and lenalidomide should be continued.

CTCAE System/Organ/Class (SOC)	ADVERSE EVENT	AGENT	ACTION**
Other	Non-hematologic AE assessed as lenalidomide related ≥Grade 3		Omit dose and follow at least weekly If the AE resolves to ≤Grade 2, implement one dose reduction step and continue therapy

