### 8.0 Dosage Modification Based on Adverse Events

Strictly follow the modifications in this table for the first cycle of combination treatment with ibrutinib, lenalidomide and dexamethasone, until individual treatment tolerance can be ascertained (**not including the treatment period where MTD of the combination is being determined as per Section 7.31**). Thereafter, these modifications should be regarded as guidelines to produce mild-to-moderate, but not debilitating, side effects. Reductions apply to treatment given in the preceding cycle and are based on adverse events observed since the prior dose.

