**ALERT:** **ADR reporting may be required for some adverse events (See Section 10)**

#### 8.1 General Considerations:

- a) Missed doses are to be omitted rather than made up, unless the dose of one of the study drugs was forgotten and remembered on the same day, in which case the dose can be taken that day. Any doses missed on a particular day are not to be made up the next day.

Doses that are considered to be vomited are not to be made up and a mention about the time of dose and time of vomiting episode should be made in the pill diary.

- b) If multiple toxicities are experienced, dose modifications will be based on the toxicity requiring the largest dose reduction.
- c) Reductions are based on the dose given in the preceding cycle and are based on toxicities with an attribution of possible, probable, or definite that were observed since the prior toxicity evaluation.
- d) If either ibrutinib or lenalidomide must be permanently discontinued, the patient will be removed from the protocol therapy.
- e) If a drug is omitted due to specific adverse events and the patient is on combination therapy, the other agents, considered unrelated to the adverse event may be continued.
- f) A dose omission of >28 days for ibrutinib or lenalidomide is not allowed. If a patient cannot be administered a dose for >28 days due to adverse events or any other reason, the patient should be removed from the study treatment and go to event monitoring.
- g) Patients will be removed from the study if we are unable to manage the adverse events they experience, and it is therefore necessary to permanently discontinue ibrutinib or lenalidomide. These events are listed in the tables in Section 8.3 and 8.5.

8.2 Dose Reductions for Phase I cycles 2 and beyond and Phase II portion (based on Adverse Events in Tables below):

8.21 The following recommended dose modifications will be utilized for ibrutinib, lenalidomide and/or dexamethasone separately as per the best judgment of which drug was most likely to have caused the toxicity:

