8.22 Dose level tables

8.221 Lenalidomide

Dose Level	Lenalidomide* Starting Dose 25 mg
1st dose reduction	20 mg
2nd dose reduction	15 mg
3rd dose reduction	10 mg
4 th dose reduction	Discontinue

\*Other than lenalidomide dose adjusted for renal dysfunction

8.222 Dexamethasone

Dose Level	Dexamethasone Starting Dose 40 mg*
1st dose reduction	20 mg
2nd dose reduction	12 mg
3rd dose reduction	8 mg
4th dose reduction	Discontinue

\*Starting dose level of dexamethasone for patients  $\geq 75$  years old will be 20mg so those patients will start with the 2nd dose reduction row.

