	$\geq$ Grade 3		
 
• Discontinue study treatment and go to event monitoring
 

Vascular disorders	Thromboembolic event $\geq$ Grade 3		
 
• Omit dose and start anticoagulation; restart at investigator's discretion (maintain dose level)
 

Immune system disorders	Allergic reaction Grade 2-3		
 
• Omit dose and follow at least weekly until resolution
 
• If AE resolves to <math>\leq</math>Grade 1, reduce dose by 5 mg and continue therapy
 

	Anaphylaxis Grade 4		
 
• Discontinue study treatment and go to event monitoring
 

Skin and subcutaneous tissue disorders	Erythema multiforme $\geq$ Grade 3		Discontinue study treatment and go to event monitoring
	Skin ulceration $\geq$ Grade 2		Discontinue study treatment and go to event monitoring
	Other: Non-blistering rash Grade 3		
 
• If Grade 3 omit dose and follow weekly until resolution
 
• If AE resolves to <math>\leq</math>Grade 2 continue therapy
 

	Other: Non-blistering rash Grade 4		
 
• Discontinue study treatment and go to event monitoring
 

Other AEs	Non-hematologic AE assessed as related to lenalidomide $\geq$ Grade 3		
 
• Omit dose and follow at least weekly until resolution
 
• If the AE resolves to <math>\leq</math>Grade 2, implement one dose reduction step and continue therapy (per Table 8.2)
 

\* Located at [http://ctep.cancer.gov/protocolDevelopment/electronic\\_applications.ctc.htm](http://ctep.cancer.gov/protocolDevelopment/electronic_applications.ctc.htm)

\*\* Use the following to describe actions in the Action column:

- Omit = The current dose(s) for the specified drug(s) during a cycle is skipped. The patient does not make up the omitted dose(s) at a later time
- Hold/Delay = The current dose(s) of all drugs during a cycle is delayed. The patient does make up the delayed dose(s) when the patient meets the protocol criteria to restart drugs.
- Discontinue = The specified drug(s) are totally stopped.

If lenalidomide has been omitted and the toxicity does not return to  $\leq$ Grade 2 within 28 days, the patient must be removed from protocol treatment and proceed to Event Monitoring.

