**Ethanol/Nutrition/Herb Interactions:**  
Ethanol: Avoid ethanol (may enhance gastric mucosal irritation).  
Food: Dexamethasone interferes with calcium absorption. Limit caffeine.  
Herb/Nutraceutical: Avoid cat's claw, Echinacea (have immunostimulant properties)

15.37 **Known potential adverse events:** Consult the package insert for the most current and complete information.  
**Common known potential toxicities,** frequency not defined: Fluid and electrolyte disturbances, congestive heart failure in susceptible persons, hypertension, euphoria, personality changes, insomnia, exacerbation of infection, exacerbation or symptoms of diabetes, psychosis, muscle weakness, osteoporosis, vertebral compression fractures, pancreatitis, esophagitis, peptic ulcer, dermatologic disturbances,

convulsions, vertigo and headache, endocrine abnormalities, ophthalmic changes, and metabolic changes. Some patients have experienced itching and other allergic, anaphylactic or hypersensitivity reactions. Withdrawal from prolonged therapy may result in symptoms including fever, myalgia and arthralgia.

15.38 **Drug procurement:** Commercial supplies. Pharmacies or clinics shall obtain supplies from normal commercial supply chain or wholesaler.

15.39 **Nursing Guidelines:**

- Monitor regularly for hypertension, CHF and other evidence of fluid retention.
- Advise patient of possible mood or behavioral changes, i.e., depression, euphoria, insomnia, even psychosis. Instruct patient to report any suspected changes to healthcare team.
- Assess for symptoms of gastric ulcer, heartburn, or gastritis. Suggest antacids. Instruct patient to report symptoms to healthcare team if unable to control.
- Evaluate signs of infection, particularly local candidal infections and treat appropriately.
- Monitor blood glucose frequently.
- Instruct patient to report frequent, unrelenting headaches or visual changes to healthcare team.
- Advise patient that easy bruising is a side effect.

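### The catch-all row of the dexamethasone dose table (Section 8.4) names lenalidomide, so it cuts dexamethasone for the other drug's events and leaves dexamethasone's own unlisted events without a rule

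*Combined protocol and SAP*

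**What the plan says.** The dexamethasone table in Section 8.4 has rows for hyperglycemia, gastrointestinal hemorrhage, pancreatitis, dyspepsia or ulcer or gastritis, arrhythmia, edema, and confusion or mood alteration. It ends with a row labelled Other, whose trigger is a "Non-hematologic AE assessed as lenalidomide related" of Grade 3 or higher. The action is to omit the dose, follow at least weekly and, once the event is at Grade 2 or lower, "implement one dose reduction step and continue therapy".

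The lenalidomide table in Section 8.3 has its own catch-all with the same trigger, "Non-hematologic AE assessed as related to lenalidomide", also at Grade 3 or higher, followed by one lenalidomide step.

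Section 8.21 governs all three drugs. It says that doses are modified "separately as per the best judgment of which drug was most likely to have caused the toxicity".

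On how binding the tables are, Section 8.0 says: "Strictly follow the modifications in this table for the first cycle of combination treatment". The period in which the MTD is being determined is excluded. It continues: "Thereafter, these modifications should be regarded as guidelines".

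**The concern.** A dose table for one drug should respond to toxicity attributed to that drug. Here the only general row of the dexamethasone table responds to toxicity attributed to lenalidomide, with two consequences.

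First, a lenalidomide-related event sets off two reductions, one in each table, although Section 8.21 would touch lenalidomide only. Two investigators facing the same event could dose the patient differently, and each could point to the protocol.

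Second, a severe non-hematologic event that the investigator attributes to dexamethasone, and that has no row of its own, meets no rule: no grade at which to act and no grade at which to restart. Phase II enrolls transplant-ineligible patients, including all those scored intermediate or frail, so rules for steroid toxicity matter in this population.

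**Working it through.** The plan states no figure on this point. The check compares the relevant texts and then does short dose arithmetic.

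**1. The two catch-all rows side by side**

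| | Section 8.3 (lenalidomide) | Section 8.4 (dexamethasone) |
|---|---|---|
| Drug blamed | lenalidomide | lenalidomide |
| Grade | 3 or higher | 3 or higher |
| Action | omit, then one step down at Grade 2 or lower | omit, then one step down at Grade 2 or lower |

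The triggers are the same. The action text of the 8.4 row matches the arrhythmia row of the same table, which belongs to dexamethasone. The action therefore fits dexamethasone and only the drug name in the trigger does not. The catch-all in Section 8.5 acts on ibrutinib and does not fill the gap.

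**2. When the row binds**

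In Phase I the first combination cycle is Cycle 1, which is the MTD-determination period and is excluded by Section 8.0. In Phase II, Section 7.12 gives ibrutinib and dexamethasone in Cycle 1 and adds lenalidomide in Cycle 2. The strict window is therefore Cycle 2, one 28-day cycle per Phase II patient. In Phase II Cycle 1 the patient takes dexamethasone without lenalidomide, so a row that requires attribution to lenalidomide cannot apply.

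**3. Size of the literal double reduction**

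Inputs: dosing days from Section 7.12; lenalidomide steps from Section 8.221; dexamethasone steps from Section 8.222 ("Dexamethasone Starting Dose 40 mg", with 20 mg as the start at age 75 or older).

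- Lenalidomide, days 1 to 21: 21 × 25 = 525 mg per cycle; one step down, 21 × 20 = 420 mg. Change: −105/525 = −20%.
- Dexamethasone under 75, four doses: 4 × 40 = 160 mg; one step down, 4 × 20 = 80 mg. Change: −80/160 = −50%.
- Dexamethasone at 75 or older: 4 × 20 = 80 mg; one step down, 4 × 12 = 48 mg. Change: −32/80 = −40%.

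The drug not held responsible loses proportionally more than the drug that is. A note after the Section 8.5 table keeps a reduction required at the start of the next cycle in place for the rest of treatment; it does not address a restart within a cycle.

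**4. Size of the gap**

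Section 15.37 lists the known toxicities of dexamethasone, among them "exacerbation of infection, exacerbation or symptoms of diabetes, psychosis, muscle weakness, osteoporosis, vertebral compression fractures". Diabetes and psychosis in that run are left out of the count, because the hyperglycemia and confusion or mood rows plausibly cover them. At least seven listed toxicities have no row in Section 8.4: hypertension, insomnia, exacerbation of infection, muscle weakness, osteoporosis, vertebral compression fractures and convulsions. For these, what remains is the investigator's judgment under Section 8.21 and the dose ladder in Section 8.222. The ladder says how far to step down, but nothing says when to act or when to restart.

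**The case against.** The strongest reply is that the surrounding rules already steer investigators correctly. Section 8.1(e) allows agents judged unrelated to an event to be continued, and Section 8.21 ties each modification to the likely cause. Together they give a stated basis for leaving dexamethasone alone after a lenalidomide-related event. That is fair, but 8.1(e) is only permissive, and it does not remove a table row that Section 8.0 says to follow strictly in the first combination cycle.

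Section 7.31 also calls for a documented discussion with the study PI before ibrutinib or dexamethasone is modified for Section 8 events in Phase I. As written, that is not confined to DLTs. The unguarded part is therefore mainly Phase II.

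The Agent cell beside the Other row is blank, so the row might be read as acting on lenalidomide. The percentages for dexamethasone would then fall away. But the row would merely repeat Section 8.3, and the gap for dexamethasone-related events would remain. The table's title and its pattern of naming the agent once for a block of rows favor dexamethasone.

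Two limits stand. The −50% and −40% come from the spacing of the dose ladder and apply only if the row is followed literally. The count of seven says nothing about frequency: Section 15.37 gives neither rates nor grades. For osteoporosis and vertebral fracture, a rule of omitting until Grade 2 and then reducing is a poor fit, and Section 1.1 lists osteoporosis and pathological fractures among the effects of myeloma itself, which makes attribution uncertain.

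**Conclusion.** The concern holds. The row is wrong as written: it duplicates the trigger in Section 8.3, conflicts with attribution by drug in Section 8.21, and leaves dexamethasone-related events without their own row with neither a trigger grade nor a recovery grade.

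The scope is limited. Events with their own row in Section 8.4 are unaffected. Phase I DLTs are handled by Section 7.31, and clotting events by the notes after the Section 8.5 table. After the strict cycle, the remaining effect is inconsistent handling between investigators. The dose percentages assume full starting doses, a first reduction and a literal reading of the row. The documents give no event rate, so no number of affected patients can be projected. Because this is an operative dosing rule in a trial that includes frail patients, it should be corrected, although the Phase II decision rule and its error rates do not depend on it.

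**What to change.** In the Other row of Section 8.4, replace lenalidomide with dexamethasone as the drug to which the event is attributed, and leave the action unchanged. Lenalidomide-related events remain covered by the catch-all in Section 8.3. The cost is one word in the protocol, with no effect on sample size, analysis or timelines.

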## 8.5 Ibrutinib Dose Modifications

→ → Use the NCI Common Terminology Criteria for Adverse Events (CTCAE) version 4.0\* unless otherwise specified ← ←

CTCAE System/Organ/Class (SOC)	ADVERSE EVENT	AGENT	ACTION**
Investigations	Neutrophil count decreased Grade 4 lasting >7 days	Ibrutinib	Omit ibrutinib** until recovery to Grade ≤1 or baseline May restart at same dose for first occurrence Each subsequent occurrence may restart at next lower dose after recovery to Grade ≤1 or baseline If AE occurs at lowest dose discontinue treatment and go to event monitoring
	Platelet count decreased Grade ≥3		
Blood and lymphatic system disorders	Febrile neutropenia ≥Grade 3	Ibrutinib	Omit ibrutinib** until fever resolves and ANC ≥1000/µL, then resume ibrutinib at the previous dose
Gastrointestinal disorders	Nausea ≥Grade 3 (if persistent despite optimal antiemetic therapy) Vomiting ≥Grade 3 (if persistent despite optimal antiemetic therapy) Diarrhea ≥Grade 3 (if persistent despite optimal anti-diarrheal therapy)	Ibrutinib	Omit ibrutinib** until recovery to Grade ≤1 or baseline May restart at same dose for first occurrence Each subsequent occurrence may restart at next lower dose after recovery to Grade ≤1 or baseline If AE occurs at lowest dose discontinue treatment and go to event monitoring
Other (Non-hematologic)****	Any other Grade 4 AE or any unmanageable Grade 3 AE	Ibrutinib	Omit ibrutinib** until recovery to Grade ≤1 or baseline May restart at same dose for first occurrence Each subsequent occurrence may restart at next lower dose after recovery to Grade ≤1 or baseline If AE occurs at lowest dose discontinue treatment and go to event monitoring

## Additional Adverse Events:

\*\* If ibrutinib is omitted in the middle of the cycle and the toxicity resolves, patient can re-start the drug but the days of drug treatment missed do not need to be caught-up and can be omitted in order to maintain the cycle schedule.

- Dose omission: Ibrutinib may be omitted for adverse event considerations for a maximum of 28 consecutive days. Study medication should be discontinued permanently in the event of AE lasting more than 28 days.
- If multiple adverse events are seen, administer dose based on the greatest reduction required by any single adverse event observed.
- Dose modifications are for adverse events attributed to study treatment only. Dose modifications are not required for adverse events if they are deemed unrelated and/or unlikely related to study treatment.

- Reductions apply to treatment given in the preceding cycle and are based on adverse events observed since the prior dose.

\*\*\*\* If cough, dyspnea, and other pulmonary symptoms occur, a chest x-ray and high-resolution chest CT scan should be obtained. Incentive spirometry studies (to include DLCO) should be considered. Consider Pneumocystis pneumonia or viral pneumonitis. Patients who experience a deep vein thrombosis (DVT), pulmonary embolus (PE), or other clotting event should have all study drugs temporarily omitted while full-dose anticoagulation is initiated (other than warfarin or other Vitamin K antagonist). There should not be a delay of more than 28 days in reinitiating the study treatment.

**NOTE:** If the patient experiences a significant adverse event requiring a dose reduction at the start of the next cycle, then the dose will remain lowered for that entire remaining length of the study treatment.

**NOTE:** Adverse events requiring a dose-reduction step for any or all drugs beyond the two dose-reduction steps (levels –1 and –2) (per Table 8.2) will be at the discretion of the treating physician, if the decision is made for the patient to be kept on study. These dose reductions must be clearly recorded in reported clinical data.

**NOTE:** For a dose omission of ibrutinib or lenalidomide of more than 28 days beyond the scheduled date of retreatment, the patient should discontinue protocol treatment and go to the event monitoring phase per Section 4.2. In the event patient is benefitting from treatment and the delay was unrelated to treatment toxicity, patient may remain on study with approval of study PI.

### **8.51 Dose Modification for Hepatic Impaired Subjects**

Ibrutinib is metabolized in the liver and therefore subjects with clinically significant hepatic impairment at the time of screening (Child- Pugh class B or C) are excluded from study participation. For subjects who develop mild liver impairment while on study (Child-Pugh class A), the recommended dose reduction for ibrutinib is to a level of 280 mg daily (two capsules). For subjects who develop moderate liver impairment while on study (Child-Pugh class B), the recommended dose reduction is to a level of 140 mg daily (one capsule). Subjects who develop severe hepatic impairment (Child-Pugh class C) must omit ibrutinib until resolved to moderate impairment (Child-Pugh class B) or better. Monitor subjects for signs of toxicity and follow dose modification guidance as needed (Refer to [Appendix XII](#)).

